# 10.2 ANALYSIS POPULATIONS

# 10.2.1 Safety (SAF) Population

All safety analyses will be performed on the SAF Population defined as all randomized subjects who receive at least one dose of ZX008 or placebo. Subjects will be analyzed according to the treatment actually received.

# 10.2.2 Modified Intent-to-Treat (mITT) Population

The mITT Population is defined as all randomized subjects who receive at least one dose of ZX008 or placebo and for whom at least one week of diary data are available. Subjects will be analyzed according to the treatment group to which they were randomized. The primary comparison of ZDX008 0.8 mg/kg/day to placebo, as well as key secondary analyses, will be performed on the mITT Population.

# 10.2.3 Per Protocol (PP) Population

The PP Population is defined as all randomized subjects who receive at least one dose of ZX008 or placebo, complete the entire 12 week Maintenance Period, and have no major protocol

Confidential Page 82 of 175

deviations that would have a significant impact on clinical outcome. Subjects will be analyzed according to the treatment they received. The primary and key secondary efficacy analyses will be repeated on the PP Population if there are substantial differences in the makeup of the mITT and PP Populations.

#### 10.3 TREATMENT GROUPS

Subjects will be randomly assigned to one of three treatment groups: ZX008 0.8 mg/kg/day, ZX008 0.2 mg/kg/day, or placebo.

### 10.4 TREATMENT PERIODS

#### **Baseline Period**

The Baseline Period covers the approximately 42-day span just prior to randomization and the start of treatment. The baseline frequency of convulsive seizures will be calculated from data collected during this period.

#### **Titration Period**

The Titration Period covers the first 14 days of treatment while subjects are titrated to their randomized dose. It begins on the first day of treatment (Study Day 1) and extends through Study Day 15 regardless of the exact day on which a subject reaches his or her assigned dose. The Titration Period applies to all subjects including placebo recipients.

#### Maintenance Period

The Maintenance Period covers the 12 weeks following the end of the titration period. It begins on Study Day 16 and extends through Study Day 99.

### Titration + Maintenance (T+M) Period

The T+M period combines the Titration and Maintenance periods, beginning on Study Day 1 and extending through Study Day 99. The T+M period is considered the treatment period.

# Follow-up Period

The Follow-up Period begins immediately at the end of T+M period and extends to a final visit 2 weeks later; ie, from Study Day 99 through Study Day 113. Only subjects who do not roll over enrollment into the open-label extension will participate in the Follow-up Period.

# 10.5 STATISTICAL ANALYSES AND METHODS

All efficacy, safety, and PK data will be summarized. Continuous data will be summarized using descriptive statistics including means, standard deviations, medians, lower and upper quartiles, and ranges. Categorical variables will be summarized with frequencies and percentages. Confidence intervals will be calculated for key parameters or estimates as warranted.

Efficacy and PK data will be summarized by treatment (ZX008, placebo) age cohort (<6 years and ≥6 years of age), as well as for the total subjects in the population.

Confidential Page 83 of 175

A complete description of the statistical analyses and methods will be available in a SAP, which will be finalized before the database is locked.

### 10.5.1 Efficacy Analyses

# 10.5.1.1 Primary Efficacy Analysis

The primary efficacy endpoint is the change in the mean convulsive seizure frequency (MCSF) per 28 days between the Baseline and T+M periods. The MCSF will be calculated from all available data collected during the Baseline or T+M Periods.

The primary endpoint will be analyzed using an analysis of covariance (ANCOVA) model with treatment group (three levels) and age group (< 6 years,  $\geq$ 6 years) as factors, and with baseline frequency as a covariate. The primary analysis will compare the ZX008 0.8 mg/kg/day group to the placebo group using a two-sided test at the  $\alpha$ =0.05 level of significance.

Since the ANCOVA used in the primary analysis relies on assumptions of normality, the primary endpoint will also be analyzed using a nonparametric method that does not require as stringent assumptions. A test such as the van Elteren test, which extends the Wilcoxon rank sum test to include stratified data, will be used to compare the ZX008 0.8 mg/kg/day group to the placebo group while stratifying for age group. If normality assumptions are not met, the results of the van Elteren test will be used to assess the primary objective.

An additional analysis will be performed to assess the sensitivity of the primary analysis to changes in dose or type of concomitant AED medications that may occur during the course of the trial, which are protocol violations. Specifically, the primary analysis will be repeated with a factor added to indicate whether a subject had a change in prescribed dose or type of concomitant AED medication during the T+M period. Further exploratory analyses may be conducted if changes in concomitant AED medication appear to have a significant impact on the primary outcome.

Additional analyses will compare the changes between the baseline MCSF and the MCSF measured independently during the Titration Period alone and the Maintenance Period alone.

### 10.5.1.2 Key Secondary Analyses

The first key secondary endpoint – the proportion of subjects who achieve a  $\geq$ 40% reduction from baseline in convulsive seizure frequency – is derived directly from the primary endpoint. That is, the proportion of subjects in the ZX008 0.8 mg/kg/day group who have a change in convulsive frequency of at least -40 percentage points will be compared to the analogous proportion in the placebo group. The comparison will be made using a logistic regression model that incorporates the same factors and covariates as the ANCOVA used in the primary analysis. The second secondary endpoint – the proportion achieving a  $\geq$ 50% reduction in convulsive seizures – will be analyzed similarly. The analyses will be performed using data collected over the T+M period.

The longest interval between convulsive seizures will be calculated for each subject over the entire T+M period. The ZX008 0.8 mg/kg/day and placebo groups will be compared using a log-rank test.

Confidential Page 84 of 175

The MCSF in the ZX008 0.2 mg/kg/day group will be compared to the placebo group using the same methods employed for the primary analysis. Analyses of other key secondary endpoints involving the ZX008 0.2 mg/kg/day group will employ similar methods as those used to compare ZX008 0.8 mg/kg/day to placebo. Whenever feasible, secondary analyses involving either ZX008 0.8 mg/kg/day or ZX008 0.2 mg/kg/day will be repeated using post-treatment data collected during the Titration Period alone and during the Maintenance Period alone.

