In the event that the study is terminated prematurely then the procedure for termination should be followed as described in Section 3.6. Concern for the interests of the subject will always prevail over the interests of the study.

The reason for, and date of discontinuation from participation in the study must be recorded in detail in the eCRF and in the subject's medical records (eg, AEs, lack of compliance, lost to follow-up, etc). If possible, the subject/subject's legal representative should confirm his decision in writing.

The investigator will attempt to complete all procedures usually required at the end of the study at the time when the subject's participation in the study is discontinued or as close as possible to that time. Specific procedures required are described in Section 6.2.9 and Section 6.3. As far as possible, a complete final examination must be performed on all subjects who do not complete the study according to the study protocol.

Data collected until the time a subject discontinues participation in the study will be handled in the same manner as data for subjects completing the study. Where possible, further information will be collected if any AEs are experienced by a subject after discontinuing participation in the study.

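### The gated 40% and 50% responder tests score each subject on whatever treatment-period diary days exist, so someone who stops after a week or two is classed exactly like a completer

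*Protocol*

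**What the plan says.** Four parts of the protocol together fix the responder rule.

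- **Section 10.5.1.1 (primary analysis):** "The MCSF will be calculated from all available data collected during the Baseline or T+M Periods". No minimum number of days is set.
- **Section 10.5.1.2 (key secondary analyses):** the 40% responder endpoint "is derived directly from the primary endpoint", and the 50% endpoint "will be analyzed similarly". On the window: "The analyses will be performed using data collected over the T+M period". The model is a logistic regression with the primary ANCOVA's factors and covariate (treatment, age group, baseline frequency), so it has no term for length of follow-up.
- **Section 10.2.2 (mITT):** membership needs one dose and extends to those "for whom at least one week of diary data are available". The text does not say that this week must be on treatment. The primary comparison, "as well as key secondary analyses, will be performed on the mITT Population".
- **Section 4.5 (removal of subjects):** data up to discontinuation "will be handled in the same manner as data for subjects completing the study".

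Section 10.4 defines the T+M period as "beginning on Study Day 1 and extending through Study Day 99". Section 10.5.1.3 places the 40% and 50% endpoints second and third in the serial sequence for 0.8 mg/kg/day. Counting on, they are sixth and seventh, for 0.2 mg/kg/day.

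**The concern.** A mean change measured over a short window is merely noisier. Once it is cut at -40% or -50%, part of that noise becomes apparent success. Section 4.3 admits subjects with 6 convulsive seizures in 42 days, about one a week. For such a child, one quiet week on treatment is a 100% reduction and a response on both endpoints.

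Under section 5.5.2, a subject in the 0.8 mg/kg/day arm reaches the target dose on Study Day 9. Someone who stops at day 7 can therefore count as a responder to a dose not yet taken.

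The responder results are confirmatory tests in a serial procedure, so misclassification also affects whether the tests below them are reached. With 35 subjects per arm, one subject is 100/35 = 2.9 percentage points of responder rate.

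**Working it through.** **The plan's own figure.** The protocol gives no figure for the responder endpoints. Its sample size reproduces: with a difference of 40 points, SD 50, two-sided alpha 0.05 and 90% power, n = 2 × (1.960 + 1.282)² × 50²/40² = 32.8, so 33 per arm (34 with the t distribution). Power at 35 per arm is 0.917 (0.910 with t). The point here does not depend on it.

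**Inputs from the protocol.** Entry rule: at least 6 convulsive seizures in 42 days and at least 2 in each 3-week half (section 4.3). T+M: 14 weeks, or 98 days (section 3.1). Arm size: 35 (section 10.1).

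**Assumed inputs.** True seizure rates of 4 to 40 per 28 days, because the protocol gives no distribution. Counts are Poisson at a constant rate, with no treatment effect. Early exits are 10-15% of an arm, because the protocol gives no dropout rate.

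**Hand check.** A subject with exactly 6 baseline seizures expects 6/42 × 7 = 1 seizure in 7 days. A 40% response needs at most 0.6 seizures, that is, none: exp(-1) = 0.37. The 50% endpoint gives the same answer.

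**Simulation.** The 42-day baseline count is drawn, the entry rule is applied, and the frequency over d treatment days is compared with 0.6 times the subject's own baseline frequency. The probability of a 40% response with no true change is:

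| True rate per 28 days | 7 days | 14 days | 28 days | 98 days |
|---|---|---|---|---|
| 4 | 0.43 | 0.45 | 0.37 | 0.25 |
| 6 | 0.39 | 0.32 | 0.23 | 0.11 |
| 12 | 0.28 | 0.19 | 0.11 | 0.03 |
| 40 | 0.11 | 0.04 | 0.01 | about 0 |

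For the 50% endpoint, 7 days against 99 days gives 0.38 against 0.13 at rate 4, 0.30 against 0.04 at 6, 0.21 against 0.005 at 12, and 0.05 against 0 at 40.

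The baseline has to be sampled. If it is treated as known, the 98-day figure at rate 4 is only 0.06. With sampling and the entry rule it is 0.25, because subjects near the minimum qualify partly on a high baseline draw and then fall back.

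**Effect on an arm's 40% responder rate.** Excess = share leaving × (probability on short follow-up − probability on 98 days).

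- *All leave near day 7.* Rate 6: 10% × (0.39 − 0.11) = 2.8 points and 15% × 0.28 = 4.2 points. Rate 4: 10% × (0.43 − 0.25) = 1.8 and 15% × 0.18 = 2.7. Rate 12: 10% × (0.28 − 0.03) = 2.5 and 15% × 0.25 = 3.8. So about 2 to 4 points. At rate 40 it is 10% × 0.11 = 1.1 to 15% × 0.11 = 1.7.
- *Exits spread evenly over days 7 to 98.* Averaging the short-follow-up probability over exit days gives 0.3 to 1.1 points for rates 4 to 20. In subjects, that is 0.003 × 35 = 0.1 to 0.011 × 35 = 0.4 per arm.

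**The case against.** **This belongs in the SAP.** Handling of discontinuation for a binary secondary endpoint is often left there, and section 10.5 promises a full description in one. That would settle the matter if the protocol were silent. It is not: it fixes the data used, the analysis set and the treatment of discontinued subjects' data, and a SAP that follows them yields this rule. Section 4.5 is about subject removal and was not written as a responder rule, but nothing elsewhere overrides it.

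**Supportive analyses help.** Section 10.5.1.2 repeats secondary analyses on the Maintenance Period alone where feasible, and a week-2 leaver has no such data. Section 10.2.3 adds a completers-only repeat if the populations differ substantially. Both are useful, but neither changes the gated tests. It is also true that the 0.8 mg/kg/day responder tests are reached only after the primary succeeds, so the rule cannot create a positive primary result.

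**Stronger readings.** A reader might infer three things that the documents do not support.

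- *That the bias favours the higher dose.* The protocol gives no withdrawal rates by arm, and placebo subjects may leave for worsening seizures (section 4.5, reason 7).
- *That a child withdrawn for worsening is the typical false responder.* Such a child normally has more seizures in the diary. With the rate doubled over 14 days, a false 40% response occurs in about 12% at 4 per 28 days, 4% at 6, 1% at 10 and about 0% at 20.
- *That clustering simply enlarges the problem.* Clustering that persists within a subject raises the full-period chance as well. With a baseline of 6 treated as known and variance μ + 0.3μ², the chance is 0.42 on 7 days against 0.29 on 99 days. Under Poisson it is 0.37 against 0.06. The gap narrows.

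**Non-responder counting is a choice.** It scores a child with a large reduction who stops late in Maintenance as a failure. That stands as a real cost and is the reason to keep the available-data version and to offer a narrower alternative.

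**Conclusion.** The point holds as a flaw in a stated rule, of modest expected size. Misclassification by chance is clearly more likely on one or two weeks than on the full period, most of all near the entry minimum, and it is small at high seizure rates.

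If early stopping is equal across arms, the result is noise and a diluted contrast. If it is unequal, the comparison shifts towards the arm with more early leavers, whichever that is.

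With 10-15% of an arm leaving, the shift is under about half a subject in 35 when exits are spread out, and at most about 1.5 subjects (4.2% of 35) if all leave near day 7. These sizes rest on a constant-rate Poisson model and on assumed seizure rates, dropout shares and exit times. The existence of the rule rests on the protocol text alone.

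**What to change.** In section 10.5.1.2, state that for the gated 40% and 50% tests, and for the 75% endpoint, a subject who discontinues before completing the Maintenance Period counts as a non-responder. Keep the available-data classification as a sensitivity analysis.

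A narrower alternative is to count as non-responders only those below a prespecified minimum of on-treatment diary days, such as 28. This removes the shortest windows but leaves some chance response: at exactly 28 days it is still 0.23 at 6 per 28 days and 0.11 at 12, against 0.39 and 0.28 on 7 days.

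The cost is one sentence before database lock and one extra run, with no change to trial conduct. The downside is a slightly conservative result for an arm with more withdrawals unrelated to efficacy, which the sensitivity analysis would show.

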#### Efficacy

Primary Efficacy Analysis: The primary efficacy endpoint is the change in the mean convulsive seizure frequency (MCSF) per 28 days during the T+M periods compared with Baseline. The MCSF will be calculated from all available data collected during the Baseline and treatment periods. The primary endpoint will be analyzed using an analysis of covariance (ANCOVA) model with treatment group (three levels) and age group (< 6 years, ≥6 years) as factors, and with Baseline MCSF as a covariate. The primary analysis will compare the ZX008 0.8 mg/kg/day group to the placebo group using a two-sided test at the alpha=0.05 level of significance. The primary endpoint will also be analyzed using a nonparametric method and if normality assumptions are not met, the results of the nonparametric analysis will be used for evaluation of the primary endpoint. An additional analysis will be performed to assess the sensitivity of the primary analysis to changes in concomitant AED medications that may occur during the course of the trial. Specifically, the primary analysis will be repeated with a factor added to indicate whether a subject had a change in concomitant AED medication during the T+M period. Safety

All safety data will be appropriately analyzed by treatment group. The number and percentage of subjects with AEs will be displayed by body system and preferred term using the Medical Dictionary for Regulatory Activities (MedDRA). Summaries in terms of severity and relationship to study drug will also be provided. Adverse Events of Special Interest (AESI) and Serious AEs (SAEs) will be summarized separately in a similar manner. Laboratory tests, vital signs, physical

Confidential Page 22 of 175

examinations, neurological examinations, ECG, Doppler echocardiogram, C-SSRS, Tanner Staging results, etc, will be summarized appropriately, by treatment. All safety summaries will be based on the Safety Population.

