# 3.5 RATIONALE FOR STUDY DESIGN AND CHOICE OF TREATMENT GROUPS

It is recognized that performing clinical studies in young children or in subjects with reduced cognitive capacity presents particular practical and ethical issues. However, given the seriousness of DS, and the possible consequences of current inadequate treatments, the use of children with DS in this study is considered justified. Stratifying the randomization by age group is considered appropriate because the frequency and severity of major seizures can be higher in younger subjects. The two strata in the study will be subjects aged below 6 years and subjects aged 6-18 years. The study design has incorporated a titration period to enable subjects randomized to the high dose group adequate time to acclimate to this dose. Following the Titration Period, subjects will enter a 12-week Maintenance Period where they will continue on their randomized dose for the remainder of the study. The 12-week duration of the Maintenance Period is in keeping with the current standard study duration for evaluating the efficacy of chronic medications. Given the individual variability in seizure frequency and seizure type in this patient population, the primary endpoint, which seeks to compare an appropriate baseline of convulsive seizure frequency to the convulsive seizure frequency following treatment, is an appropriate primary endpoint for efficacy in this population.

Subjects will receive investigational medicinal product (IMP; ZX008 or placebo) in addition to their existing antiepileptic medications at their stable doses throughout the entire study. Thus, subjects receiving placebo will not be denied active therapy; they will continue to receive their existing medications at the exact same dosages. As the principal study measurement (convulsive seizures) might be considered subjective, a double-blind study design will prevent subjective bias. Upon study completion, eligible subjects will be able to receive ZX008 in an open-label extension study for up to 1 additional year of treatment.

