### 5.5 TREATMENT ADMINISTRATION

### 5.5.1 Randomization

Upon completion of the Baseline Period, subjects who qualify for the study will be randomized (1:1:1) in a double-blind manner to receive 1 of 2 doses of ZX008 (0.2 mg/kg/day, 0.8 mg/kg/day; 30mg/day maximum) or placebo. The randomization will be stratified by age (<6 years, ≥6 years) to ensure balance across treatment arms, and at least 40% of subjects will be in each age group. Subjects will be assigned a randomization number by the IVR/IWR system upon confirmation that subject qualifies for enrollment in the Titration Period. Once a randomization number is assigned to a subject, the site will record the subject's initials and identification number on the corresponding study drug bottles. Each bottle will contain the assigned treatment (ZX008 0.2 mg/kg/day, ZX008 0.8 mg/kg/day, or placebo). ZX008 and placebo will be identical, thus rendering the study drug and placebo indistinguishable. For each IMP bottle and randomization number assigned, the following information will be recorded on the drug

Confidential Page 45 of 175

accountability form: subject initials, unique bottle number, date each bottle is assigned, and drug used and unused during the study.

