### 10. STATISTICS

#### 10.1 DETERMINATION OF SAMPLE SIZE

The results of the only randomized, placebo-controlled studies in subjects with Dravet syndrome can be found in the European Public Assessment Report (EPAR) for stiripentol (EMA, 2007). The EPAR summarizes the results from two studies: STICLO France and STICLO Italy. In the stiripentol groups, the SD of the percentage change in seizure frequency from baseline to month 2 was 42% in the French trial and 26% in the Italian trial. The analogous SDs for placebo groups were 38% and 62%. An SD of 50% was assumed for the primary analysis in this trial comparing ZX008 0.8 mg/kg/day to placebo on the change from baseline in seizure frequency. Using a two-sided test at the  $\alpha$ =0.05 significance level, a sample size of 35 subjects per treatment group affords 90% power to detect a difference in mean change from baseline of 40 percentage points. Similar assumptions and calculations yield a requirement for an additional 35 subjects in the 0.2 mg/kg/day ZX008 group. Thus, the total sample size is planned to be 105 subjects (35 per arm).

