# 10.5.1.3 Multiplicity Strategy and Testing Hierarchy

The efficacy analyses will employ a serial gatekeeper strategy to maintain the Type 1 error rate at  $\alpha$ =0.05 across the family of analyses that support the primary and key secondary objectives. The strategy specifies a hierarchy of significance tests where each test acts as a gatekeeper to the tests below it.

The primary and key secondary endpoints will be assessed in the following order beginning with comparisons of ZX008 0.8 mg/kg/day to placebo on

- The change in MCSF from baseline.
- The proportion of subjects who achieve a ≥40% reduction from baseline in convulsive seizure frequency.
- The proportion of subjects who achieve a ≥50% reduction from baseline in convulsive seizure frequency.
- The longest convulsive seizure-free interval.

The evaluation of key secondary endpoints continues by comparing the ZX008 0.2 mg/kg/day group to placebo in the following order:

- The change in MCSF from baseline.
- The proportion of subjects who achieve a ≥40% reduction from baseline in convulsive seizure frequency.
- The proportion of subjects who achieve a ≥50% reduction from baseline in convulsive seizure frequency.
- The longest convulsive seizure-free interval.

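### The log-rank test for the longest seizure-free interval carries no age term, unlike every other confirmatory analysis, and may cost power at the step before all 0.2 mg/kg/day tests

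*Protocol*

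**What the plan says.** On randomisation, Section 5.5.1 states: "The randomization will be stratified by age (<6 years, ≥6 years) to ensure balance across treatment arms". Neither stratum may make up less than 40% of the sample. Section 3.5 gives the reason for stratifying: "Stratifying the randomization by age group is considered appropriate because the frequency and severity of major seizures can be higher in younger subjects".

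The confirmatory methods treat age as follows:

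- **Change in convulsive seizure frequency (10.5.1.1):** an ANCOVA with age group as a factor. The nonparametric alternative, van Elteren, is stratified by age group.
- **≥40% and ≥50% responders (10.5.1.2):** logistic regression with the ANCOVA's factors and covariates, so age is included.
- **Longest convulsive seizure-free interval (10.5.1.2):** "The ZX008 0.8 mg/kg/day and placebo groups will be compared using a log-rank test". Age is not mentioned. The 0.2 mg/kg/day comparison is to use similar methods.

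Section 10.5.1.3 sets a fixed order in which "each test acts as a gatekeeper to the tests below it". The 0.8 mg/kg/day longest-interval test is fourth, and the four 0.2 mg/kg/day tests follow it.

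**The concern.** A higher seizure rate shortens the longest gap between seizures. If younger children have more seizures, age is therefore prognostic for this endpoint as well as for seizure frequency. A log-rank test that pools the two age groups leaves that variation in the comparison. Because randomisation balances age across arms, pooling does not bias the test towards a false claim. It makes the test conservative and weakens it.

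A miss at this step blocks every formal claim for 0.2 mg/kg/day, including its effect on convulsive seizure frequency, which Section 2.2 lists first among the key secondary objectives.

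**Working it through.** **1. The plan's own figure.** Section 10.1 states "An SD of 50% was assumed for the primary analysis in this trial" and "a sample size of 35 subjects per treatment group affords 90% power to detect a difference in mean change from baseline of 40 percentage points". The synopsis sets the primary comparison "using a two-sided test at the alpha=0.05 level of significance".

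- n per arm = 2 × (1.960 + 1.282)² × (50/40)² = 32.8, so 33 by the normal approximation, or 34 with the t distribution.
- Power at 35 per arm = Φ(40 / (50 × √(2/35)) − 1.960) = Φ(1.387) = 91.7%, or 91.0% with the t distribution.

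The stated 35 per arm and 90% are reproduced. They concern the primary endpoint only. The protocol gives no effect size, power or age effect for the longest interval, so every treatment and age effect below is an assumption.

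**2. Log-rank power with no age effect.** With 70 subjects and every interval observed, Schoenfeld's formula gives power = Φ(|ln HR| × √(70/4) − 1.960).

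- HR 0.50: Φ(0.693 × 4.183 − 1.960) = Φ(0.940) = 82.6%.
- HR 0.45: Φ(0.799 × 4.183 − 1.960) = Φ(1.380) = 91.6%.

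**3. Pooled against age-stratified, exponential times.** Let U be the sum of observed minus expected events and V its variance. The pooled statistic is U/√V over all subjects. The stratified one is (U₁ + U₂)/√(V₁ + V₂) over the two age groups. Settings: 35 per arm, half aged <6, no censoring, 40,000 runs per cell (Monte Carlo error about √(0.8 × 0.2/40,000) = 0.2 points).

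| Age HR | HR 0.50: pooled | HR 0.50: stratified | Change | HR 0.45: pooled | HR 0.45: stratified | Change |
|---|---|---|---|---|---|---|
| 1.0 | 80.1% | 78.5% | −1.7 | 89.8% | 88.5% | −1.3 |
| 1.25 | 79.6% | 78.5% | −1.1 | 89.2% | 88.5% | −0.8 |
| 1.5 | 78.3% | 78.6% | +0.3 | 88.1% | 88.4% | +0.2 |
| 2.0 | 73.6% | 78.1% | +4.5 | 85.6% | 88.7% | +3.1 |
| 3.0 | 66.5% | 78.8% | +12.3 | 79.4% | 88.5% | +9.1 |

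Changes are from unrounded values. With 40% aged <6, the minimum share in Section 5.5.1, the pattern is the same. At HR 0.50 the change is −1.8 points at age HR 1, +3.5 at 2 and +10.0 at 3.

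**4. Null rejection in the same model.** With half aged <6, the pooled test rejects 5.6% at age HR 1, 4.4% at 2 and 3.4% at 3. The stratified test rejects 5.4% to 5.6% throughout. The pooled test becomes conservative as age becomes more prognostic.

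**5. Seizure-process models.** Poisson seizures with lognormal subject rates; the endpoint is the longest gap over the treatment period.

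| Assumptions | Age ratio 1 | 1.5 | 2 | 3 |
|---|---|---|---|---|
| Log-SD 0.9 plus extra variation on treatment, 40% reduction (1,500 runs) | 48.3 vs 47.3 | 45.6 vs 45.5 | 46.7 vs 48.5 | 43.0 vs 49.1 |
| Same, 50% reduction | 73.1 vs 72.5 | 70.5 vs 70.9 | 70.8 vs 72.3 | 68.7 vs 74.0 |
| Log-SD 0.6, 40% reduction (1,000 runs) | 78 vs 78 | 74 vs 77 | 69 vs 78 | 56 vs 76 |
| Log-SD 0.8, 50% reduction | 82 vs 82 | 83 vs 85 | 80 vs 83 | 72 vs 83 |
| Log-SD 1.0, 50% reduction | 69 vs 70 | 64 vs 66 | 64 vs 68 | 59 vs 67 |

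Entries are power in percent, pooled vs stratified. With 1,000 to 1,500 runs, each has a Monte Carlo error of a little over 1 point.

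**6. Effect of the entry criterion.** Section 4.3 requires at least 6 convulsive seizures in the 6-week baseline, with at least 2 in each half. This removes low-rate subjects, mostly from the older group. At age ratio 2, with an assumed base rate of 10 per 28 days and 800 runs:

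- Log-SD 0.6, 40% reduction: 65.5% vs 75.3% without the criterion, 78.3% vs 83.4% with it.
- Log-SD 0.6, 50% reduction, with the criterion: 94.5% vs 97.1%.
- Log-SD 0.9, with the criterion: 60.3% vs 64.3% (40% reduction) and 87.3% vs 88.6% (50% reduction).

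In the first setting the gap falls from 9.8 to 5.1 points. Across settings with the criterion, the change was about −1 to +3 points at ratios up to 1.5, +1 to +7 at 2 and +5 to +18 at 3.

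**The case against.** The strongest reply is that the protocol names a test family and is silent on strata. Section 10.5 leaves the complete methods to an SAP, and the summary of Amendment 1 says the statistical sections were aligned with one. The SAP may therefore already stratify. That stands in part: nothing in 10.5.1.2 is false, and a reader who infers that the protocol forbids stratification goes beyond the text. It does not dispose of the point. The protocol does not leave this test open; it names it, and it brings age into each of the other confirmatory methods. On the page this test differs from the rest, on a choice that changes its p-value.

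Three stronger readings are tempting, and the documents support none of them:

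- **That the test is invalid.** It is not. Null rejection stays near or below nominal, so the Type 1 error of the hierarchy is not threatened.
- **That a large loss is certain.** Section 3.5 says only that seizure frequency can be higher in younger subjects and gives no size. Simulated gaps such as 65% vs 78% at a twofold age ratio, or 45% vs 80% at fourfold, come from low between-subject spread, a modest treatment effect and no entry criterion. They are unfavourable corners, not expected losses.
- **That stratifying is free.** With no age effect it costs up to about 2 points.

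It is also fair that this step matters only after the primary and both responder tests have succeeded. Trials that get so far tend to show larger effects, where the gap is smaller. The figures above are unconditional power, not the added chance of losing the 0.2 mg/kg/day claims.

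**Conclusion.** The point holds as one of efficiency and consistency. The confirmatory longest-interval test is written without the factor used to stratify randomisation, although every other confirmatory method includes it, and it precedes all 0.2 mg/kg/day tests.

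Stratifying changes power by about −2 to +3 points for age ratios up to 1.5, about +1 to +9 at 2 (just under 10 in one setting without the entry criterion) and about +5 to +20 at 3. These figures rest on 35 per arm, the assumed treatment effects and between-subject spread, no censoring, and an age effect that the protocol does not quantify. The direction is secure if age is prognostic; the size is not.

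**What to change.** In 10.5.1.2, state that the longest-interval comparison uses a log-rank test stratified by the randomisation age group (<6, ≥6 years), for 0.8 and 0.2 mg/kg/day alike. The age-stratified van Elteren test already named in 10.5.1.1 would also serve. One of the two should be fixed before unblinding, and the SAP should match.

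This is one sentence of wording, with no change to sample size, data collection or the order of tests. The statistical cost is at most about 2 points of power if age turns out not to matter.
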